4. STUDY POPULATION

4.1 Population (base)

Study population:

Only patients that provide written informed consent will be included. They will first have to review the instruction video that explains and shows how the capillary blood collection and separation of plasma should be done. If the patient is still willing to participate after he has seen the instruction video and received all information by the research team, he will receive the self-testing kit with all materials needed to send in 4 plasma samples over a period of 2 years. The patients will be offered HCV RNA self-testing for 2 consecutive years and thus during 400 patient years of follow-up. Recruitment will stop when at least 1 plasma sample is received from 200 patients. Therefore, we estimate that we will need to include 225 to 250 patients to have an evaluable population of at least 200.

We allow HIV+ as well as HIV- MSM to be included as long as they fulfill the in- and exclusion criteria. HIV negative MSM can only be included if they are taking PREP and if HCV RNA testing is not done as the standard of care HCV diagnostic strategy at the PREP clinic but ALT testing is done as an HCV testing policy no more often than 3x/years. Twice yearly testing is the standard of care in HIV+ patients in the Netherlands but the frequency may be higher or lower in HIV uninfected PREP users per local policy (e.g. in Belgium).

The total number of patients that was informed about the study and the number of patients that reviewed the video but who never actually started using the HCV RNA self-test will be used to evaluate the acceptability of HCV RNA self-testing.

For the statistical analysis the following populations are defined:

Modified Intention to treat population (MITT):

All patients who signed the informed consent, received the HCV RNA self-test kit and in which the HCV RNA test at the screening visit was negative.

Per protocol population (PP):

All patients who signed the informed consent, received the HCV RNA self-test kit and in which the HCV RNA test at the screening visit was negative and who collected all 6 monthly plasma samples during the entire follow-up.

4.2 Inclusion criteria

In order to be eligible to participate in this study, a subject must meet all of the following criteria:

- Cured of HCV defined as an SVR (=documented negative HCV RNA test) at least 12 weeks after the end of DAA therapy *and* no new documented positive HCV RNA test after the date of the SVR

OR

Spontaneous clearance of HCV infection defined as two consecutive negative HCV RNA tests at least 3 months apart after a positive HCV RNA test.

- In care for an HIV infection in an HIV clinic in a study center or HIV negative and receiving PrEP at a PrEP clinic
- Able and willing to perform the self-test at home after viewing the instruction video
- Willing to fill out a questionnaire on risk behavior at the time of HCV self-testing
- At risk of HCV re-infection according to a short questionnaire, in other words, patients should have one of the following risk factors (19):
 - Receptive unprotected (condomless) anal intercourse in the last 6 months
 - Fisting or being fisted without gloves in the last 6 months
 - Sharing toys in the last 6 months
 - Syphilis or LGV in the last 12 months,
 - Slamming (injecting drug use) in the last 12 months
 - Sharing sniffing straws or other objects to sniff drugs in the last 12 months

4.3 Exclusion criteria

A potential subject who meets any of the following criteria will be excluded from participation in this study:

- Age < 18
- Patients that are tested by HCV RNA as a standard of care test (e.g. in the context of PREP use) > 1x/year
- Patients that are expected to be tested by ALT at their HIV or PREP clinic <1x/year

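### The criteria lists allow once-yearly routine HCV RNA testing (which 4.1 appears to bar for PrEP users), but the virtual-control rule ignores it and so overstates control time for some men

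*Combined protocol and SAP*

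**What the plan says.** **Eligibility.** Section 4.1 makes inclusion of HIV-negative men on PrEP conditional. They qualify only "if HCV RNA testing is not done as the standard of care HCV diagnostic strategy at the PREP clinic" and provided that "ALT testing is done as an HCV testing policy no more often than 3x/years". It adds that testing frequency in PrEP users may differ from twice a year under local policy.

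The formal lists are looser. The only inclusion criterion in 4.2 that concerns the care setting is "In care for an HIV infection in an HIV clinic in a study center or HIV negative and receiving PrEP at a PrEP clinic", with no condition on the testing policy. Section 4.3 has two exclusions on testing: "Patients that are tested by HCV RNA as a standard of care test (e.g. in the context of PREP use) > 1x/year" and "Patients that are expected to be tested by ALT at their HIV or PREP clinic <1x/year". The first tolerates RNA once a year, for any participant. The second sets a floor for ALT and no ceiling.

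**Virtual control.** Section 3 takes standard care to be ALT every 6 months, with RNA only after an ALT elevation. For a man found by self-test, it assigns the control diagnosis to the next clinic visit (about +3 months) if his ALT is raised at confirmation. If his ALT is normal, it assigns the visit after that (about +9 months). Neither section 3 nor section 10 says what happens if he also has a routine RNA test due.

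**The concern.** The control arm is not observed; it is built by rule from the self-test-detected men. Its validity depends on the rule matching how each man would have been diagnosed without the self-test.

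A routine RNA test would find the infection whatever the ALT. For a normal-ALT man whose yearly RNA test is due at the +3-month visit, the +9-month assignment gives him a control time he would not have had. The error can only lengthen the control time, so it can only enlarge the apparent benefit. Section 10 makes the size of the reduction (at least 2 months) the focus of the study, so a one-directional error in that size matters even if the test result does not change.

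The mismatch between 4.1 and 4.2/4.3 adds to this. It leaves unclear which PrEP users belong in the study, and sites could apply different rules.

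**Working it through.** **1. Which men pass which section**

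| Routine testing | 4.1 | 4.2/4.3 lists |
|---|---|---|
| PrEP user, standard-of-care RNA once a year | barred, if yearly RNA counts as the clinic's strategy | pass |
| PrEP user, ALT 4 or more times a year | barred | pass |
| PrEP user, RNA 2 or more times a year | barred | excluded |
| HIV-positive man, RNA once a year | PrEP condition does not apply | pass |

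**2. The plan's own example (section 3).** Last negative test at month 6, positive self-test at month 9:
- infection date = 6 + (9 − 6)/2 = 7.5 months; actual time = 9 − 7.5 = 1.5 months
- ALT raised: virtual time = 12 − 7.5 = 4.5 months; gain = 3 months
- ALT normal: virtual time = 18 − 7.5 = 10.5 months; gain = 9 months

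These agree with the plan.

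**3. The normal-ALT case with yearly routine RNA**
- RNA due at month 12: virtual time = 12 − 7.5 = 4.5 months; gain = 3, not 9. Overstated by 6 months.
- RNA due at month 18: virtual time stays 10.5 months; gain = 9. No error.

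**4. How often each occurs.** Table 12 (section 8.3) puts home self-tests at months 3, 9, 15 and 21. If routine RNA falls at months 12 and 24, the next RNA test is +9, +3, +9 and +3 months away. If it falls at months 6, 18 and 30, the sequence is +3, +9, +3 and +9. An equal split is therefore reasonable when RNA is taken at the ALT visits, but it is an assumption. The mean normal-ALT gain is 0.5 × 3 + 0.5 × 9 = 6 months.

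**5. Mean gain among self-test-detected men with yearly RNA.** Let q be the share with normal ALT at confirmation. Section 1 gives 25% (range 10 to 40%) for persistently normal levels in chronic infection; applying it to recent re-infection is an assumption.
- plan's rule: 3(1 − q) + 9q
- allowing for yearly RNA: 3(1 − q) + 6q
- difference: 3q

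| q | Plan's rule (months) | With yearly RNA (months) | Difference (months) |
|---|---|---|---|
| 10% | 3.6 | 3.3 | 0.3 |
| 25% | 4.5 | 3.75 | 0.75 |
| 40% | 5.4 | 4.2 | 1.2 |

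**6. Effect on the overall mean.** Let p be the share of self-test-detected re-infections in men with yearly RNA. The mean gain falls by 3qp: 0.75p months at q = 25%, and 0.3p to 1.2p across 10 to 40%. The documents do not give p. For illustration, p = 10% gives 0.075 months, about 2 days (0.03 to 0.12 months across the range). Section 4.4 expects 200 × 2 × 4% = 16 re-infections. If all 16 entered the mean, one misassigned man would move it by 6/16 = 0.375 months.

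**7. More frequent ALT (illustration).** Take the self-test midway between ALT visits, and diagnosis at the next visit (ALT raised) or the one after (ALT normal):
- ALT every 6 months: gain 3 or 9 months
- ALT three times a year, allowed by 4.1: 2 or 6 months
- ALT four times a year, barred by 4.1 but not by 4.3: 1.5 or 4.5 months

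A fixed 6-monthly schedule would credit all these men with 3 or 9 months.

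**The case against.** **Section 4.1 still binds.** It is current protocol text, worded as mandatory, and can be read as an extra condition for PrEP users on top of the lists. That stands. A reader might infer that sites will enrol men whom 4.1 bars; the documents support only that a site working from the lists alone could. The risk is not idle: section 8.3 moves a patient forward once he meets the inclusion and exclusion criteria, and the limits are not there.

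**Yearly RNA may not be the clinic's strategy.** Section 4.1 speaks of clinic policy, 4.3 of how often a patient is tested. A clinic that relies on ALT and adds one RNA test a year might satisfy both. This is arguable, although 4.3 itself calls that test standard of care. The ALT limb has no such ambiguity. It would also be wrong to infer that the lists let in any amount of routine RNA testing, since 4.3 excludes more than once a year.

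**The bias does not come from the mismatch.** This is correct. It comes from the section 3 rule. It also reaches HIV-positive men with yearly RNA, and 4.1 itself allows ALT three times a year. Copying 4.1 into the lists would not produce a purely 6-monthly, ALT-only control.

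**Real visit dates may already be intended.** Section 3 refers both to the next planned visit and to the next 6-monthly one. If each man's own dates are used, most of the ALT-frequency error goes. The RNA error stays.

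**The effect may be small.** It may be, because p is unknown and section 4.4 plans the sample in terms of HIV-positive men.

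**Conclusion.** The point holds in a limited form. Sections 4.1 and 4.2/4.3 do not state the same limits, and the virtual-control rule makes no provision for a routine RNA test that the criteria permit. For a normal-ALT man with yearly RNA, the control time is overstated by 0 or 6 months, never understated.

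The fall from 4.5 to 3.75 months applies only among self-test-detected men with yearly RNA. It rests on the equal split between visits and on a normal-ALT share borrowed from chronic infection. For the trial as a whole the effect scales with p and cannot be sized from the documents.

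A reader might infer that the primary comparison is overturned. The documents do not support that. A man's gain drops from 9 to 3 months at most under the 6-monthly schedule, so this error does not change the sign of any paired difference in the Wilcoxon signed rank test. Even at p = 100% the mean gains (3.3 to 4.2 months) exceed the 2-month relevance threshold. What is affected is mainly the estimated size of the reduction.

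**What to change.** 1. Reconcile 4.1 with 4.2/4.3, so that one rule on routine RNA and on ALT frequency applies and stands in the lists that sites screen from. Which limits to keep is for the sponsor to decide.
2. Add to section 3 and section 10: for any enrolled man, HIV-positive or PrEP user, the virtual diagnosis date is the earlier of his next planned routine RNA test and the ALT-based date, both taken from his own planned visit schedule rather than a fixed 6-monthly one. Say also whether the normal-ALT delay is counted as the second planned visit or as about 9 months, because the two differ off a 6-monthly schedule.
3. Record each man's routine RNA and ALT schedule before his self-test result is known, so that the virtual date cannot depend on the result.

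The cost is a wording change, an addition to the analysis rule and an extra item on the case record form. The estimated reduction may come out slightly smaller and, depending on how the sections are reconciled, a few PrEP users may become ineligible.

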4.4 Sample size calculation

200 HIV+MSM with a previously cured or a spontaneously resolved HCV infection will be included. These patients will be offered HCV RNA self-testing for 2 years and thus during at least 400 patient years of follow-up.

Previous reports on the incidence of HCV re-infection have observed a re-infection incidence of 5 to 15% per year. However, we should also consider that after the roll-out of DAA therapy in the Netherlands a 51% decrease in the number of acute HCV infections was observed in 2016 compared with 2014. Therefore, we estimate that the incidence of re-infection will be 4% rather than 5-15% per year. Therefore, we anticipate to diagnose a HCV re-infection in 8% of the patients during the 2 years of follow-up. With the inclusion of 200 patients and an average follow-up of 2 years per patient, we should therefore be able to diagnose 16 re-infections. The calculator for a continuous outcome superiority trial of the website sealedenvelope.com was used for the sample size calculation because the outcome we measure is continuous (days).. Now assuming a time from re-infection to diagnosis of 4.5 months or 135 days (SD of 2 months or 60 days) with the current standard of care ALT testing strategy (virtual control group) and a reduction to 2.5 months or 75 days with the HCV RNA self-testing intervention, the required sample size is 16 infections per arm. Because these 16 infections will be used to calculate the time to diagnosis for the intervention as well as for the control group, a sample size of only 16 infections will give the study 80% power to show a difference between the intervention and the virtual control group.

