3. STUDY DESIGN

Single arm open label multicenter study.

We consider a single arm open label multicenter study the most appropriate design, given the relatively small patient population at risk for HCV re-infection in the Netherlands. Indeed, the number of HIV+MSM that fulfill the in- and exclusion criteria (see below) in the participating Dutch study centers is estimated at 250-350, of which a subset will be interested in study participation. Three additional Belgian study centers and one Swiss center have also agreed to participate in the study. Even with the participation of these foreign HIV treatment centers, a randomized fully powered study remains unachievable. Indeed, if the time to diagnosis would be reduced from 4.5 to 2.5 months with the intervention and assuming a standard deviation of 2 and an 80% power and alfa of 5%, the study would need to include 2 groups of patients in which a minimum of 16 re-infections would be diagnosed in each group (see sample size calculation below). With an incidence of HCV re-infections of $\pm 8\%$ during the 2 years of follow-up this would mean that 2×200 patients need to be included to diagnose 2×16 re-infections. As our most optimistic inclusion scenario will allow recruitment of 250

patients in 2 years, this means that a single arm study with 200 patients will already take 4 years to complete given the follow-up time of 2 years of each of the patients. Therefore, we consider a single arm open label multicenter study the most appropriate.

For the purpose of the analysis, we will use the study population as its own “virtual” control group (see below for a more detailed explanation of this control group).

[figure not shown]
Intervention:

The self-test that is used to detect HCV RNA is performed every 6 months on top of standard of care ALT test as described above. The HCV RNA testing will be done at home by the patient 3 months after each HIV outpatient clinic visit and sends the plasma sample to our laboratory by regular post mail. If HCV RNA is detected, the treating physician will be informed and the patient contacted immediately and invited to visit the outpatient clinic for confirmation of the positive HCV RNA self-test and evaluation of liver enzymes. If the presence of HCV RNA is confirmed, HCV therapy can then be initiated according to the Dutch or Belgian HCV treatment guideline.

Standard HCV diagnostic procedures in the “virtual control group”:

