The standard of care HCV re-infection diagnostic strategy used by HIV outpatient clinics is measuring ALT levels every 6-months. If an ALT elevation is documented, HCV RNA testing is performed to diagnose a potential HCV re-infection. If this HCV RNA test is positive, HCV therapy can then be initiated according to the Dutch HCV treatment guideline.

Figure 1 illustrates the timing of the home-based HCV RNA test in the intervention group; The self-test is done every 6 months in between the ALT tests at the outpatient HIV clinic. Furthermore, the self-test is done at the screening visit as well to exclude that patients with an undiagnosed HCV infection are included.

Figure 1.

Defining the time to diagnosis in the intervention and the virtual control group:

Patients diagnosed with an HCV re-infection by the HCV RNA self-test are contacted immediately by the site investigator and invited to visit the outpatient clinic to have their liver enzymes tested and to confirm the HCV diagnosis with a whole blood HCV RNA PCR test. If at that time the ALT level is elevated, we will assume that an HCV RNA test would have been done by the treating physician at the next 6-monthly HIV outpatient clinic visit (in \pm 3 months) and therefore the HCV diagnosis would have been made at that time point.

In patients diagnosed with an HCV re-infection in which the ALT level turns out to be normal, we will assume that the ALT level would *not be elevated* at the next planned HIV outpatient visit (in general \pm 3 months later), but that it *would be elevated* at the consecutive HIV outpatient clinic visit (in general \pm 9 months later) and therefore the HCV diagnosis would have been made at that time point. This conservative approach that assumes an ALT elevation in all patients 9 months after the positive HCV RNA test is needed because we anticipate that all patients will have started HCV therapy within 6 months after diagnosis and this leads to prompt ALT normalization. Therefore, we cannot use the actual measured ALT level 9 months after the positive HCV RNA test.

[figure not shown]

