The date of infection is estimated as the midpoint between the date of last negative HCV test and the date of the first positive HCV test. The last negative HCV test can be either a negative ALT test or a negative HCV RNA test. The first positive HCV test can be either a positive HCV RNA self-test or a positive whole blood HCV RNA test performed in the hospital. This estimation of the date of infection will be used for the analysis of the time to diagnosis in both the intervention and the virtual control group.

This is illustrated by the following example and in figure 2. A study patient with a positive HCV RNA self-test 9 months after the start of the study had an ALT within the normal range at 6 months. When he is informed about the positive self-test and the positive test is confirmed by the local investigator his ALT is measured as well and turns out to be elevated. For this patient, the date of infection is estimated at 7.5 months ($6+((9-6)/2)$). The actual time to re-infection diagnosis in the intervention arm is (9-7.5) or 1.5 month. To evaluate the time to re-infection diagnosis as part of the “virtual” control group, we will disregard the result of the self-test at 9 months and assume that at 12 months an elevated ALT would have been detected, because his ALT was also elevated at 9 months. Therefore, the virtual time to re-infection diagnosis for this patient is (12-7.5) or 4.5 months (scenario 1 in figure 2). However, if the ALT level of this patient would have been normal at 9 months, the virtual time to re-infection diagnosis would be different. Indeed, while the actual time to re-infection diagnosis would still be 1.5 month, the virtual time to re-infection diagnosis would be (18-7.5) and therefore 10.5 months because we will assume that ALT would still be normal at the 12 months HIV outpatient clinic visit but would have become elevated at the next consecutive HIV outpatient clinic visit at 18 months (scenario 2 in figure 2).

[figure not shown]
Please note that all patients will undergo an HCV RNA self-test at the time of screening for the study. This will not only allow for the demonstration of the self-test by the trial-nurse but will also ascertain that patients with an undiagnosed chronic HCV are not included.

Figure 2

Scenario 1

Scenario 2

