10. STATISTICAL ANALYSIS

For the primary endpoint the time to HCV re-infection diagnosis will be compared between the intervention group ("The self-testing strategy") and the virtual control group ("The standard of care ALT-based strategy"). Descriptive statistics will be used to quantify the difference in time to diagnosis between these groups. The focus of this study is the feasibility of the diagnostics and therefore to show that the amount of reduction in time to diagnose that the test will lead to is sufficient (i.e. at least 2 months, see paragraph 4.4) to be considered clinically relevant. Since the actual time to diagnosis and the virtual time to diagnosis are measured and estimated for the same patient, these data are dependent. Consequently, for inferential statistics, the Wilcoxon signed rank test will be used in which the virtual time to diagnosis is considered the pre-intervention measurement and the actual time to diagnosis as observed with the self-test intervention will be considered the post-intervention measurement.

The time to diagnosis is defined as the number of days between the calculated time of transmission and the first positive HCV RNA test.

The calculated time of transmission is defined as the midpoint between the date of the last negative and first positive HCV test. For this purpose, the last negative HCV test can consist of a normal ALT level or a negative HCV RNA test.

The analysis of the primary endpoint will be done according to the intention to treat approach and will therefore include the MITT population as described above.

We refer to p.17 for a detailed explanation on how to define the date of the first positive HCV test in the virtual control group.

The analysis of secondary endpoint 1 is similar to the methodology described for the primary endpoint. For the secondary endpoints 2 to 4 descriptive statistics will be used and 95% confidence intervals will be reported.

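### The 2.5-month self-testing input and common SD of 2 months behind the 80% power do not follow from the plan's own dating rule, which gives 1.5 months when tests are kept

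*Combined protocol and SAP*

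**What the plan says.** Section 3 argues feasibility "if the time to diagnosis would be reduced from 4.5 to 2.5 months with the intervention", "assuming a standard deviation of 2 and an 80% power and alfa of 5" percent. Section 4.4 repeats the inputs: "4.5 months or 135 days (SD of 2 months or 60 days") under standard care and "a reduction to 2.5 months or 75 days with the HCV RNA self-testing intervention, the required sample size is 16 infections per arm". It concludes that 16 re-infections, each used for both strategies, give 80% power. Neither section says where 2.5 months comes from.

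Section 3 also defines the endpoint. Infection is dated halfway between the last negative and the first positive test, and a normal ALT counts as negative. On timing: "The self-test is done every 6 months in between the ALT tests at the outpatient HIV clinic". Table 12 in section 8.3 puts self-tests at months 3, 9, 15 and 21 and ALT at 6, 12, 18 and 24. In the worked example the infection is dated at 7.5 months, and "The actual time to re-infection diagnosis in the intervention arm is (9-7.5) or 1.5 month". The virtual control time is 4.5 months if ALT is elevated (scenario 1) and 10.5 months if it is normal (scenario 2).

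Section 10 asks whether the reduction "is sufficient (i.e. at least 2 months, see paragraph 4.4) to be considered clinically relevant". The primary analysis uses the MITT population, which under section 4.1 does not require any home sample to have been sent.

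**The concern.** The calculation takes 4.5 months from scenario 1 but pairs it with 2.5 months, a value that no scenario produces. The same scenario pairs 4.5 with 1.5. The event target, the 80% power and, through the cross-reference in section 10, the 2-month relevance criterion all lean on this pair.

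The endpoint is close to discrete: the schedule and the virtual-control rule fix what each man can contribute. What varies is whether the self-test was done and whether ALT was normal. If the calculation contains neither quantity, its power figure says little about the trial's chance of success.

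**Working it through.** **1. The plan's figure.** Inputs from sections 3 and 4.4: difference 135 - 75 = 60 days, SD 60 days, alpha 5%, power 80%. For two independent means, two-sided: n = 2 × (60 × (1.960 + 0.842)/60)² = 15.7, so 16 per group. Power with 16 is 80.7% by the normal approximation. Expected events: 200 × 0.04 × 2 = 16. The stated figures reproduce.

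**2. What the dating rule gives.** Kept tests are 3 months apart, so the time to diagnosis is 3/2 = 1.5 months whichever test finds the infection. This also holds when a normal ALT has overlooked it, because that ALT counts as the last negative. If the self-test was missed and the clinic finds the infection, the gap is 6 months and the time is 6/2 = 3.0 months.

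Gains for men found by self-test are 4.5 - 1.5 = 3 months (ALT elevated) or 10.5 - 1.5 = 9 months (ALT normal). For men found at the clinic I take the gain as 0, because both strategies then share the diagnosis date. The plan does not spell this case out.

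**3. What a mean of 2.5 requires.** Let s be the share dated at 3.0 months: 1.5(1 - s) + 3.0s = 2.5 gives s = 2/3. If every ALT is elevated and a fraction a of self-tests is done, the mean is 3 - 1.5a, so a = 1/3. By simulation over 0-40% normal ALT, the mean is 2.2-2.4 months at a = 40% and 2.5-2.7 at a = 20%. So 2.5 implies roughly 20-40% completion.

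**4. The SD.** Times of 1.5 and 3.0 months have SD 1.5 × √(s(1 - s)), which is 0 with all tests kept and at most 0.75. An SD of 2 does not fit the self-test times. For the virtual control times at full completion, the simulated SD is 1.5-3.8 months.

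**5. Direction.** Using scenario 1's own pair (4.5 and 1.5 months) and keeping SD 60 days: n = 2 × (60 × 2.802/90)² = 6.98, so 7 per group, and 16 would give 98.9% power. Zero gains pull the other way.

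**6. Mean gain and chance of significance.** Assumptions: infections uniform over 24 months, RNA self-test detects every infection, all 6-monthly clinic visits kept, ALT status persistent within a man, 16 re-infections observed. The normal-ALT range of 10-40% is quoted in section 1 for chronic infection; 0% is added as a bound. No gain is negative, so an exact two-sided signed-rank test that drops zeros reaches p < 0.05 only with at least 6 non-zero differences (2/2⁵ = 0.0625; 2/2⁶ = 0.031). The last column is the binomial chance of at least 6 in 16.

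| Self-tests done | Normal ALT | Mean actual (months) | Mean virtual (months) | Mean gain (months) | Share found by self-test | P(at least 6 of 16) |
|---|---|---|---|---|---|---|
| 100% | 0% | 1.5 | 3.0 | 1.5 | 0.50 | 89% |
| 100% | 10% | 1.5 | 3.7 | 2.2 | 0.54 | 94% |
| 100% | 25% | 1.5 | 4.7 | 3.2 | 0.61 | 98% |
| 100% | 40% | 1.5 | 5.8 | 4.3 | 0.68 | over 99% |
| 60% | 0% | 2.1 | 3.0 | 0.9 | 0.30 | 34% |
| 60% | 10% | 2.1 | 3.6 | 1.5 | 0.35 | 51% |
| 60% | 25% | 2.0 | 4.4 | 2.4 | 0.43 | 75% |
| 60% | 40% | 1.9 | 5.4 | 3.5 | 0.52 | 92% |

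Check of the full-completion rows: men with persistently normal ALT infected after month 21 are not found, so 7/8 of that group are. With normal-ALT share q, the mean gain is [0.5(1 - q) × 3 + (7/8)q × 9] / [(1 - q) + (7/8)q], which is 1.50, 2.16, 3.19 and 4.26 for q = 0, 10, 25 and 40%. If normal ALT instead varies independently by visit, the gains for 10/25/40% are about 2.0/2.7-2.8/3.7 months at full completion and 1.2/1.8/2.6 at 60%.

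The planned pair is approached (4.4 and 2.5 months, gain 1.9) near 20% completion with 40% persistently normal ALT.

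**7. Other ALT frequencies.** Section 4.3 excludes only men expected to have ALT less than once a year, and section 4.1 allows a different frequency in PrEP users. With ALT at months 12 and 24 and every test kept, half the follow-up lies in 6-month gaps, so the mean actual time is 0.5 × 1.5 + 0.5 × 3.0 = 2.25 months.

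**The case against.** The strongest defence is that 2.5 months need not be a forecast. Section 10 calls 2 months clinically relevant, so 2.5 may simply be 4.5 minus the smallest reduction worth having, and a target difference need not equal the expected mean. That reading is possible and would justify the 2 months. The plan does not state it, however, and it would not rescue the SD or the power figure, which still describe a distribution that the endpoint does not have.

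Three further objections stand and limit the point.

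- A reader might infer that 2.5 months is impossible. It is not: the MITT population includes men who miss self-tests, and less frequent ALT also lengthens the gaps.
- A reader might infer that neither input has a basis. The 4.5 is exactly the scenario 1 control value, and a mean virtual time near it arises at full completion with about 25% normal ALT.
- A reader might infer that a 2-month gain is out of reach. At full completion the mean gain is about 2 months or more across 10-40% normal ALT.

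It is also fair that the significance chances depend on using the exact test, which the plan does not specify. With five equal gains, a continuity-corrected normal approximation gives z = (15 - 7.5 - 0.5)/√11.25 = 2.09, p about 0.04, so the threshold could be five rather than six.

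**Conclusion.** The point holds as an inconsistency between the sample-size inputs and the endpoint definition. On the 6-monthly ALT schedule the dating rule gives 1.5 months for every re-infection found with no test missed. The 2.5 is not derived and implies that most self-tests are missed, and the SD of 2 months does not fit the self-test times.

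It is tempting to conclude that the trial is underpowered. The documents do not support that: the mismatch runs both ways. Scenario 1's own pair would need fewer events, and with full completion the chance of enough non-zero differences is about 90% or higher. With 60% completion it is about 34-92%, depending on the normal-ALT share. What can be said is that the 80% corresponds to no scenario the plan describes.

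The sizes rest on uniform infection times, perfect RNA detection, kept clinic visits, zero gain for clinic-found cases and 16 observed re-infections. The derivation of 1.5 and 3.0 months needs only the plan's rule and nominal visit dates.

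**What to change.** In sections 3 and 4.4, replace 2.5 months and the common SD with values derived from the dating rule. State the assumed self-test completion and normal-ALT share, and how a clinic-found re-infection enters the comparison. Restate the 80% as the power of the planned paired signed-rank test over that range, naming the version of the test. Note the effect of the other ALT frequencies that sections 4.1 and 4.3 permit.

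In section 10, either state that the 2-month criterion applies to the mean over all MITT re-infections, zero gains included, or justify 2 months as a minimum relevant difference that does not depend on the 2.5 input.

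The cost is wording and a short calculation, with no change to enrolment or conduct. The drawback is that the single power figure becomes a range.
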